8.3.2 COPD Exacerbation Assessment

Guidelines for Identifying COPD Exacerbations for this study are located in Section 11.6.

8.3.3 Health Outcomes

The schedule for all health outcomes assessments are provided in the SoA (Section 1.3).

During Study Visits

All patient reported outcomes administered during study visits should be administered at the beginning of a study visit before any physical activity or spirometry, except for Healthcare Utilization assessment, which can be done at any point during the visit. The following is the recommended order *as applicable for a given visit*:

- mMRC
- SGRQ
- EQ-5D-5L
- Baseline/Transitional Dyspnea Index (BDI)/TDI

8.3.3.1 *St. George's Respiratory Questionnaire*

The SGRQ Patient Reported Outcome (PRO) measure is designed to assess health-related quality of life in patients with COPD in terms of symptoms, daily activity limitation, and psychosocial well-being (Jones, 1991). The SGRQ is completed by the patient.

8.3.3.2 *EuroQol-5-Domain Questionnaire*

The EQ-5D-5L questionnaire is a standardized instrument designed to measure health utility in terms of mobility, self-care, usual activities, pain/discomfort, and anxiety/depression (Szende, 2014). The EQ-5D-5L questionnaire is completed by the patient.

8.3.3.3 *Baseline Dyspnea Index/Transitional Dyspnea Index*

The BDI is used to measure the severity of dyspnea in patients at baseline (Mahler, 1984). Mahler also developed the TDI which measures changes in patient dyspnea from baseline. The instruments are scored based on ratings for functional impairment, magnitude of task, and magnitude of effort. The BDI and TDI are administered by site staff via patient interview.

8.3.3.4 *Healthcare Utilization*

All unscheduled visits to a physician office, visits to urgent care, visits to emergency department, and hospitalizations for any cause and/or related to COPD will be recorded in the eCRF. In addition, visits and contacts that are due to a COPD exacerbation will be assessed at each clinic visit and recorded in the exacerbation form of the eCRF.

8.3.3.5 *Patient Perception Survey*

At the Follow-up contact, the study site will survey each patient regarding patient perception of their study treatment assignment.

At Home

8.3.3.6 *Evaluating-Respiratory Symptoms Questionnaire*

The E-RS is a PRO instrument derived from the EXACT-PRO designed to collect data to quantify the severity of respiratory symptoms across domains of breathlessness, chest symptoms and cough/sputum in patients with COPD and evaluate treatment benefit (EXACT 2013). The E-RS is an electronic instrument to be completed by the patient in the form of the EXACT-PRO in the eDiary each evening before bedtime.

8.4 Safety Assessments

Planned timepoints for all safety assessments are provided in the SoA, Section 1.3.

8.4.1 Vital Signs

- Vital signs should be obtained prior to blinded study medication dosing at all visits.
- Temperature in Celsius, pulse rate, blood pressure, and respiratory rate will be assessed. The mode of temperature collection should be noted in the source (e.g. oral, forehead, etc).
- Blood pressure and pulse measurements will be assessed with a completely automated device. Manual techniques will be used only if an automated device is not available.
- Supine blood pressure, respiratory rate, and pulse measurements should be obtained after the patient has been at rest for at least 5 minutes in the supine position and located in a quiet setting without distractions (eg, television, cell phones).

8.4.2 Electrocardiogram

12-lead ECG will be obtained using standardized ECG equipment provided by the centralized vendor. Albuterol/salbutamol should be withheld for at least 4 hours prior to ECG assessments. It is recommended that ECG assessments should be obtained after patients have rested for approximately 5 minutes.

- The central ECG vendor will provide an ECG manual with additional instructions and details.
- All ECGs will be reviewed and over-read by the central ECG vendor and the ECG vendors interpretation of the measurement(s) will override the interpretation by the investigative site, if a consensus is not reached.

8.4.2.1 Day 1/Randomization/Visit 1: Triplicate ECGs at Pre-Dose

At Day 1/Randomization/Visit 1 prior to dosing (pre-dose), triplicate ECGs (over a brief period of time) must be performed.

8.4.2.2 Clinically Significant Abnormality

Review the ECG Withdrawal Criteria. If a clinically significant ECG abnormality is identified post-randomization, even if the assessment was pre-dose, the ECG Withdrawal Criteria in Section 11.5 should be reviewed and triplicate ECGs (over a brief period of time) should be performed to confirm the abnormality in 2 of 3 measurements.

8.4.2.3 Recommendation/ Request

Patients should refrain from smoking and/or caffeinated beverages prior to ECGs for the withholding periods below:

- *Smoking*: No smoking for at least 1-hour prior to each ECG assessment.
- *Caffeinated Beverages*: Abstain from drinking beverages with high levels of caffeine (eg, tea, coffee) for 2 hours prior to each ECG assessment.

8.4.3 Clinical Laboratory Assessments

See Section 11.3 for the list of clinical laboratory tests to be performed and additional instructions.

8.4.3.1 COVID-19

Testing for COVID-19 may optionally be completed. Patients with a positive COVID-19 test result indicating an active infection anytime during the study will be withdrawn.

8.4.4 Adverse Event Assessment

The method of detecting AE will be performed as described in Section 8.7 and Section 11.7.

8.5 Other Assessments and Procedures

Planned timepoints for all other assessments and procedures are provided in the SoA, Section 1.3.

8.5.1 Concomitant Medication Assessment

Patients must be queried for concomitant medication use at each contact (clinic visit or phone contact). Concomitant medications must be documented in the eCRF. Concomitant medications/therapy and documentation are described in Section 6.7. The list of permitted rescue and background medications is provided in Section 6.7.2. The list of prohibited medications/therapy is provided in Section 6.7.3.

8.5.2 Interactive Response Technology

Sites will enter information into the IRT at specified visits. All patients consented will be assigned a patient identification number upon signing of the informed consent.

8.5.3 Randomization

Patients meeting all inclusion criteria (Section 5.1) and all Randomization Criteria (Section 5.3) and meeting none of the exclusion criteria (Section 5.2) will be randomly assigned to blinded study medication via the IRT (Section 8.5.2) at Visit 1.

8.5.4 Electronic Diary Activities

Electronic Diary (eDiary) training will be conducted. Patients will be instructed to enter their daily symptoms (E-RS:COPD/EXACT-PRO questionnaire), administration of their blinded study medication (morning and evening), rescue medication (puffs per day), and maintenance LAMA or LABA medication, or LAMA/ICS or LABA/ICS (if applicable) into the eDiary each day. Electronic Diary compliance will be visually reviewed by the site staff at each clinic visit or discussed with the patient via phone contact and/or when patients are unable to come into the clinic. Patients with poor compliance should be instructed by the site staff to improve eDiary compliance.

8.5.5 Nebulizer Equipment Training

Patients and site staff will be trained on use of the PARI LC Sprint nebulizer and PARI Vios PRO Aerosol Delivery System, and the PARI BOY compressor or equivalent which will be used for inhalation of blinded study medication during the study period. Once the site staff has been trained, they will review the information and instructions provided by the manufacturer with the patient (e.g. Instructions for Use, located in the Pharmacy Manual). Hands on training with the nebulizer will occur at randomization with administration of the first dose of blinded study medication.

8.5.6 Training for Spirometry

Training for spirometry maneuvers will be conducted by the site staff as per the guidelines in the spirometry manual provided by the central spirometry vendor.

8.5.7 Blinded Study Medication Dosing in the Clinic

Blinded study medication dosing in the clinic will be conducted as described in Section 6.1.1.

8.5.8 Dispense/Collect Rescue Albuterol/Salbutamol

Albuterol/salbutamol will be dispensed/collected at specified visit for use as needed. See Section 6.7.1 for additional detail.

8.5.9 Dispense/Collect Blinded Study Medication

Blinded study medication will be dispensed/collected at clinic visits that include Spirometry.

8.5.10 Pharmacokinetics

All randomized patients will participate in pharmacokinetics.

8.5.10.1 Collection of Samples

A limited (sparse) sampling strategy to collect samples of whole blood will be implemented for the determination of ensifentrine in human plasma for PK assessment. Blood samples for the determination of plasma concentrations ensifentrine will be taken by venipuncture or indwelling catheter at the times specified in the SoA (Section 1.3). Up to 7 blood samples will be collected from each patient across visits at Weeks 6, 12, 24, and/or early termination visit. A sparse sampling collection scheme will be followed with sample collection times being different between even and odd numbered sites. The PK collection timepoints and associated windows are detailed by visit in Table 9 below:

Table 9: PK Collection Timepoints and Window Relative to Ensifentrine Dosing

| Visit Number | Visit Week | Odd Sites [a] | Even Sites [a] |
|-------------------|------------|--------------------------|--------------------------|
| 2 | 6 | 1.5 hours[b] | 1.0 (± 0.5) hours |
| | | 4 (± 1) hours | 2.5 (± 0.5) hours |
| 3 | 12 | 0.5 (± 0.25) hours | Pre-dose (-0.5 hours) |
| | | 3 (± 0.5) hours | 4 to 6 hours |
| | | 6 to 8 hours | 8 to 12 hours |
| 5 | 24 | Pre-dose (-0.5 hours) | Pre-dose (-0.5 hours) |
| | | 1.0 (± 0.5) hours | 1.5 hours[b] |
| ET/ withdrawal | | At the time of visit [c] | At the time of visit [c] |

a. Sample collection range is provided for samples scheduled on Week 12 at ≥ 4 hours to provide flexibility for collection at the later sampling time points.

b. The samples scheduled at 1.5 hours post-dose should be collected immediately (within 10 minutes) following the simultaneously scheduled ECG collection.

c. This sample should only be collected if the patient has received ensifentrine within the last 48 hours.

Abbreviations: ET=early termination; ECG=electrocardiogram; PK=pharmacokinetic

Approximately 4 mL of whole blood per time point for PK will be collected. The exact date/time of each blood sample collection will be recorded in the patient's eCRF. Blood samples for PK analyses should be collected in appropriate blood collection tubes as defined in the PK laboratory manual. The Sponsor or designee will provide the Investigator with a manual containing details for the preparation of blood samples to be collected. Detailed sample collection, labeling, storage, and shipment information will be described in the Laboratory Manual.

8.5.10.2 Recording of Medications and Information Specific to the Pharmacokinetic Procedures and Sample Analysis

Paper Diary

In addition to the information on blinded study medication, LAMA and/or LABA medication, and rescue albuterol/salbutamol collected in the e-Diary (Section 8.5.4) and concomitant medication information collected as described in Section 6.7, the information in Table 10 will be collected by the patient on a paper diary for the two (2) full calendar days prior to each PK collection visit. This information will be transcribed into the PK eCRF module, the concomitant medication eCRF module, or both, as applicable:

Table 10: Recording of Medications and Information Specific to Pharmacokinetics

| Medication and Time Period | Collect |
|--|---|
| For all medications that are administered for the 2 full calendar days immediately prior to each PK collection visit: | Medication name, dose (eg. Dose unit, route, schedule/frequency) Start Date and Start Time Date and Time of all doses taken prior to collection of the PK Sample |
| Blinded study medication administered the morning and the evening for the two full calendar days immediately prior to the PK collection visit: | Date Nebulization Start Time Nebulization End Time Any missed or partially administered (eg, nebulization not complete) blinded study medication administration timepoints within 2 days prior to a PK collection visit. |
| Abbreviations: PK=pharmacokinetic | |

Collection of medication and associated information in the eCRF

Medication and associated information collected in eCRF modules will include, but not be limited to the following information:

- Subject Number/Visit Number/Study Week
- All medications administered for the 2 calendar days immediately prior to each PK collection visit and administered during the PK collection visit:
 - Medication information including but not limited to the medication name, dose, dose unit, route, schedule/frequency
 - The start date and start time or ‘continuing.’ ‘Continuing’ can be selected if:
 - 1) the medication name, dose, dose unit, route, schedule/frequency are documented exactly the same as documented in the concomitant medication eCRF,
 - 2) the start date is prior to the 2 days before the PK collection visit, and
 - The stop date(s) and stop time(s) of the last dose taken prior to collection of a PK sample at any PK collection sampling timepoint on the day of a PK collection visit.
- Blinded study medication history for the 2 calendar days immediately prior to each PK collection visit which includes, but are not limited to the details below:
 - The start date, nebulization start time, and nebulization end time of blinded study medication each morning and each evening.
 - Response to the question at each dosing time “Was administration of the blinded study medication completed (yes/ no)?” If the response is “no,” the reason for interruption should be documented.
 - Response to the question “Were there any missed or partially administered (eg, nebulization not complete) blinded study medication administration timepoints (yes or no)?” If the response is “yes,” the length of the interruption should be recorded in minutes and the reason for the interruption should be documented.

- Dosing of blinded study medication during each PK collection visit must include the following information as applicable for a given PK collection visit:
 - Morning Dose:
 - The start date and nebulization start time of blinded study medication.
 - Response to the question “Was administration of the blinded study medication completed (yes/ no)?” If the response is “no,” the reason for interruption should be documented.
- PK Sample Collection
 - The date and time of each PK blood sample collected for PK analysis must be recorded.

8.5.10.3 Determination of Drug Concentration

Samples for the determination of plasma PK for ensifentrine will be analyzed on behalf of the Sponsor using appropriate validated analytical methods. Full details of the bioanalytical methods will be described in a separate Bioanalytical Report. All samples from patient assigned to treatment with ensifentrine during the study that are within the known stability of ensifentrine at the time of planned analysis by the bioanalytical laboratory will be analyzed; samples obtained from placebo patients will not be analyzed. Drug concentration information that may unblind the study will not be reported to study centers or blinded personnel until the study has been unblinded. Only the bioanalytical laboratory and unblinded biostatistician(s) who generate the randomization schedule may be unblinded to patient treatment assignment prior to database lock (DBL).

8.5.11 Genotyping/ Phenotyping

Genetic variation may impact a patient’s response to study treatment, susceptibility to, and severity and progression of disease. Variable response to study treatment may be due to genetic determinants that impact drug absorption, distribution, metabolism, and excretion; mechanism of action of the drug; disease etiology; and/or molecular subtype of the disease being treated.

Since it is known that ensifentrine is metabolized by cytochrome P450 (CYP) isozymes 2C9 (primary) and also 2D6, assessment of genetic variation will include the assessment of CYP2C9 phenotype and CYP2D6 phenotype of patients.

The results of this pharmacogenetic research will be reported separately and will not form part of the Clinical Study Report (CSR).

Approximately 8 mL of blood for DNA isolation will be collected from patients who have consented to participate in the genotyping/phenotyping analysis component of the study. Participation is optional. Patients who do not wish to participate in the genotyping/phenotyping research may still participate in the study.

In the event of DNA extraction failure, a replacement genotyping/phenotyping blood sample may be requested from the patient. Signed informed consent will be required to

obtain a replacement sample unless it was included in the original genotyping/phenotyping consent.

These samples may be stored for up to 1-year after the genotyping/phenotyping analysis has been completed.

Details on processes for collection and shipment and destruction of these samples can be found in the genotyping/phenotyping laboratory instructions.

8.5.12 Biomarker Collection

Collection of samples for other biomarker research is also a part of this study. Approximately 10 mL of blood for biomarker research is required and will be collected from all patients in this study as specified in the SoA (Section 1.3).

Analysis of interleukin (IL)-6, IL-8, and C-reactive protein (CRP) will be conducted to evaluate the effect of ensifentrine on inflammatory biomarkers (Section 11.3).

8.6 Disaster Contingencies

Prospective planning is required for this study due to the increased risk of a regional or global disaster (eg pandemic, natural disaster, terrorism).

8.6.1 Site-Level Disaster Plan

It is recommended that investigative sites prepare a written Disaster Plan for this study which describes how the site will manage patient activities and procedures in the event that site is not operating normally, site equipment is not available, and/or patient(s) cannot attend an in-clinic study visit. This written Disaster Plan could include but not be limited to a description of how the following activities and procedures will be conducted for remote visits or phone/video contact:

- Phlebotomy collection
- Vital signs collection
- Blinded study medication distribution
- Rescue albuterol/salbutamol distribution

8.6.2 **Unscheduled Visit**

8.6.2.1 ***Blinded Study Medication and/or Rescue Medication***

If blinded study medication and/or rescue albuterol/salbutamol cannot be dispensed at a scheduled clinic visit or if a patient will likely run out before attending a scheduled clinic visit, the medication may be dispense alternatively in line with according to local requirements.

Blinded study medication and/or rescue medication can be collected, and compliance can be assessed at the next in-clinic visit.

8.6.2.2 ***Study Supplied Nebulizer Replacement***

If a study supplied nebulizer cannot be distributed at a scheduled clinic visit or if the study supplied nebulizer requires replacement before attending a scheduled clinic visit, the study supplied nebulizer may either be picked-up by the patient directly outside the clinic, sent to the patient's home via trackable mail/postal service (unless restricted by local requirements), or given to the patient at the next scheduled visit.

8.6.2.3 ***Other Contingencies***

- eDiary: In the event of a problem with the eDiary or the paper diary for recording of medications and information specific to the PK procedures and sample analysis, a replacement eDiary and/or paper diary may either be picked-up by the patient directly outside the clinic or sent to the patients home according to local requirements.
- Rescue medication (albuterol/salbutamol): In the event that albuterol/salbutamol is in short supply/not available in a given country or region, another medication may be substituted following consultation and approval by the Medical Monitor (unless restricted by local requirements).
- COVID-19 Testing for Active Disease: A COVID-19 test may be conducted anytime a patient is suspected/exhibiting signs of active disease. If a COVID-19 test is positive for active disease, see Section 7.1.6 for next steps and Section 8.7.9 for AE and other reporting.
- Information relating to disruption of study participation due to COVID-19 will be captured in the eCRF (eg, reason for implementation of contingency measures, reason for missing data and relationship to COVID-19).

8.7 **Adverse Events**

The definitions of an AE or SAE can be found in Section 11.7.

Adverse events will be reported by the patient.

The Investigator and any designees are responsible for detecting, documenting, and recording events that meet the definition of an AE or SAE and remain responsible for following up AEs that are serious, considered related to the blinded study medication or study procedures, or that caused the patient to discontinue the study (Section 11.7).

As stated in Section 8.1.3, medical and COPD condition(s) identified during the Screening Visit will be documented as medical history and not as an AE unless the condition worsens during the study and meets the definition of an AE.

8.7.1 Time Period and Frequency for Collecting AE and SAE Information

AEs and SAEs will be collected from time of first dose of blinded study medication through the follow-up contact with one exception. Serious Adverse Events assessed as related to study participation (eg, study treatment, protocol-mandated procedures, invasive tests or change in existing therapy) will be collected from the time of consent through the follow-up contact.

All SAEs will be recorded and reported to the Sponsor or designee within 24 hours, as indicated in Section 11.7. The Investigator will submit any updated SAE data to the Sponsor designee within 24 hours of it being available.

Investigators are not obligated to actively seek AE or SAE after conclusion of the study participation. However, if the Investigator learns of any SAE, including a death, at any time after a patient has been discharged from the study, and he/she considers the event to be reasonably related to the blinded study medication or study participation, the Investigator must promptly notify the Sponsor.

The method of recording, evaluating, and assessing causality of AE and SAE and the procedures for completing and transmitting SAE reports are provided in Section 11.7.

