7.2 Study Participation After Discontinuation of Blinded Study Medication

Patients may permanently discontinue blinded study medication before the end of the study if they choose to or at the investigator's discretion.

Patients who permanently discontinue blinded study medication are not required to withdraw from the study unless they test positive for COVID-19 active disease. Patients who have permanently discontinued blinded study medication but do not test positive for COVID-19 active disease and have not withdrawn consent may continue in the study and complete all remaining protocol specified visits.

The Investigator must document the reason for discontinuation of blinded study medication in the eCRF.

Ideally, patients who have permanently discontinued blinded study medication will continue to attend scheduled clinic visits and complete important efficacy and safety assessments. However, if this is not possible then the investigator will encourage the patient to select one of the three options below to participate in as much of the study as they are willing (or able) to participate:

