7.2.1 Reduced Assessments

The patient continues to follow the SoA (Section 1.3) and completes only the following assessments:

- Spirometry
- SGRQ
- COPD exacerbation
- AE
- Concomitant medication

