7.2.2 Combination of Phone Contact and Reduced Assessments

The site contacts the patient by phone per the SoA (Section 1.3) to complete the following assessments:

- COPD exacerbation
- SAE
- Concomitant medication

In addition, the patient returns to the clinic at Week 24 to complete the following assessments:

- Spirometry
- SGRQ
- COPD exacerbation
- SAE
- Concomitant medication

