7.2.3 Phone Contact Only

The site contacts the patient by phone per the SoA (Section 1.3) to complete the following assessments:

- COPD exacerbation
- SAE
- Concomitant medication

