17.1. ADVERSE EVENTS

Adverse Events (AEs) will be coded using MedDRA central coding dictionary. The version of MedDRA to be used will be specified prior to database lock.

Treatment-emergent adverse events (TEAEs) are defined as AEs that started or worsened in severity on or after the first dose of study medication. Laboratory or ECG findings from procedures or samples drawn prior to the first doses of study medication that are assessed/overread after randomization will be considered pre-treatment.

In the case where it is not possible to define an AE as treatment-emergent or not, the AE will be classified by the worst case; i.e. treatment-emergent.

See Appendix 2 for handling of partial dates for AEs.

An overall summary of number of patients within each of the categories described in the subsection below, will be provided as specified in the shells. In addition, the number of patients with each of the following AE events will be presented by SOC and PT and summarized by treatment group and different period (i.e. Treatment period, Follow-up and Overall):

- TEAE
- TEAEs causally related to study medication

- Serious TEAEs
- TEAEs with an outcome of death
- TEAEs leading to discontinuation of blinded study medication
- TEAEs leading to withdrawal from study (TEAEs with a diagnosis of COVID-19, TEAEs with no diagnosis of COVID-19)
- TEAEs by maximum severity

AEs will be identified by using the “Adverse Events” page of the eCRF. Listings will include TEAEs and Non-TEAEs.

Treatment period is defined as the period from the date and time of first dose up to the date and time of last dose.

Follow-up is defined as the period from after the date and time of last dose up to the last date recorded on the study.

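### Two of the three off-drug follow-up options list only SAEs although Protocol 8.7.1 requires all AEs, so new non-serious events enter the Follow-up and Overall tables under uneven collection

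*Protocol*

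**What the plan says.** **General rule.** Protocol 8.7.1: "AEs and SAEs will be collected from time of first dose of blinded study medication through the follow-up contact with one exception". The exception concerns SAEs judged related to study participation, which "will be collected from the time of consent through the follow-up contact". It widens collection and does not mention patients off drug.

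**Patients off drug.** Under Protocol 7.2, patients who have permanently stopped study drug, are not COVID-19 positive and have not withdrawn consent "may continue in the study and complete all remaining protocol specified visits". If full attendance is not possible, "the investigator will encourage the patient to select one of the three options below":

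- 7.2.1: "The patient continues to follow the SoA (Section 1.3) and completes only the following assessments". The list includes AE.
- 7.2.2: phone contacts with a list that has SAE and not AE. Then, "In addition, the patient returns to the clinic at Week 24 to complete the following assessments", and that clinic list also has SAE and not AE.
- 7.2.3: "The site contacts the patient by phone per the SoA (Section 1.3) to complete the following assessments". The list has SAE and not AE.

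**Analysis.** SAP 17.1 defines a TEAE by its start or worsening at or after first dose and sets no end relative to last dose. It tabulates TEAEs by Treatment period, Follow-up and Overall. "Follow-up is defined as the period from after the date and time of last dose up to the last date recorded on the study". SAP 7.3 imputes no safety data.

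**The concern.** A site cannot satisfy both instructions as written. If it follows the 7.2.2 or 7.2.3 list to the letter, it collects less than 8.7.1 requires. If it follows 8.7.1, it goes beyond the list. Sites may resolve this differently.

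The inconsistency then reaches the tables. A patient on either option stays in the safety set, and the off-drug time belongs to the Follow-up period up to the last recorded date. For that patient, the absence of a new non-serious event may mean that none occurred or that nobody asked. The SAP does not flag, separate or cut off such time, and its list of changes from the protocol (SAP 3.3) does not mention it.

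What is at stake is how the Follow-up and Overall tables of non-serious events are read. If the share of patients in SAE-only follow-up differs by arm, those counts are under-ascertained unequally. One possible route is Protocol 11.6.7, which has study treatment stopped after a second or a severe exacerbation: if the drug affects exacerbations, entry to off-drug follow-up would differ by arm. The direction cannot be known in advance.

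**Working it through.** The plan gives no figure on this point, so there is none to reproduce. The check is a comparison of text, followed by an illustration of scale.

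**1. Which events are listed, and where**

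| Place | Contact | AE item listed |
|---|---|---|
| Protocol 8.7.1 | all, first dose to follow-up contact | AEs and SAEs |
| Protocol 7.2.1 | scheduled visits | AE |
| Protocol 7.2.2 | phone contacts | SAE |
| Protocol 7.2.2 | Week 24 clinic visit | SAE |
| Protocol 7.2.3 | phone contacts | SAE |

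Three lists across two options conflict with 8.7.1.

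**2. When the gap opens.** Protocol 7.1 asks patients who permanently stop drug, other than for a positive COVID-19 test, to complete the Section 7.3 assessments as soon as possible. The Schedule of Activities has an AE assessment at the early termination visit. The gap therefore opens mainly after that visit.

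**3. Which events are exposed.** SAEs are listed under every option. For an AE already reported, Protocol 8.7.3 requires proactive follow-up at later visits and contacts. What remains is non-serious events with new onset.

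**4. Which tables are exposed**

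- Treatment period (first to last dose): not exposed, because the 7.2 options begin only after drug is stopped.
- Serious TEAEs and TEAEs with a fatal outcome: not exposed in any period.
- Follow-up and Overall tables of all TEAEs, related TEAEs, TEAEs by maximum severity, and the overall summary: exposed.

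**5. Scale, on assumptions.** The documents give neither the share of patients stopping drug nor the share choosing each option. The 25% in Protocol 9.2 is a threshold for withdrawal from the study, not a rate of stopping drug. Let d be the share stopping drug and s the share of those on 7.2.2 or 7.2.3. Assume that they stop at Week 12 on average and stay to Week 24, so that half of the 24 weeks is off drug.

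- Patients = 800 × d × s
- Share of planned person-time = d × s × 12/24

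| d | s | Patients | Share of person-time |
|---|---|---|---|
| 5% | 25% | 800 × 0.05 × 0.25 = 10 | 0.0125 × 0.5 = 0.6% |
| 10% | 50% | 800 × 0.10 × 0.50 = 40 | 0.05 × 0.5 = 2.5% |
| 25% | 75% | 800 × 0.25 × 0.75 = 150 | 0.1875 × 0.5 = 9.4% |

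In patient-weeks, out of 800 × 24 = 19,200 planned, the ends of the range are 10 × 12 = 120 and 150 × 12 = 1,800. This is time under uneven solicitation, not a count of missed events.

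**The case against.** The strongest reply is that SAE appears in all three lists, which looks deliberate. Section 7.2 aims to keep in contact patients who would otherwise leave, and a shorter list is a reasonable price. The options are also fallbacks, with full attendance described as the ideal. This stands as a possible explanation of intent, but 8.7.1 does not reflect it and the SAP does not allow for it. Reduced burden is also a weak reason at the 7.2.2 Week 24 visit, where the patient is already in clinic for spirometry and the SGRQ. Nor does it fit easily with the Schedule of Activities, which has an AE assessment at the Week 18 phone contact.

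A second reply is that 8.7 and 8.7.1 still apply, so investigators must record any AE they detect. Section 8.7.2 favours open-ended questions, and the phone lists include concomitant medication, recorded with its reason for use. This also stands. A reader might infer that non-serious events in these patients are never captured, or that the reaction that led to stopping is lost. The documents support neither: there are indirect routes, and reported or related AEs must be followed up (8.7, 8.7.3). The defect is inconsistent solicitation, not absence of capture.

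A third reply is that safety analysis is descriptive (Protocol synopsis; SAP 17), so no formal comparison is put at risk. That limits the consequence, but arms are still compared by eye in these tables.

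**Conclusion.** The inconsistency is real. Protocol 7.2.2 and 7.2.3 conflict with 8.7.1, and SAP 17.1 builds the Follow-up and Overall tables as if collection were uniform. The consequence is confined to new-onset non-serious events arising after the early termination assessments, in patients on two fallback options.

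A reader might go further and conclude that the AE tables as a whole are unreliable, or that the comparison between arms is biased. The first is contradicted by the unaffected Treatment-period and serious or fatal tables. The second would need stopping or option choice to differ by arm, and the documents give no rates and no distribution of reasons for stopping. It is likewise unsupported that most of these patients stopped because of an AE.

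The range of about 0.6% to 9.4% of planned person-time rests wholly on the assumed inputs. The point merits correction because the fix is cheap and removes an avoidable ambiguity in safety data, not because a large effect has been shown.

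**What to change.** **Preferred.** Reconcile the passages by replacing SAE with AE in both lists of 7.2.2 and in the list of 7.2.3, to match 7.2.1 and 8.7.1. The same contacts are used, with no new visit or form. The cost is a change of wording in three lists and a slightly longer call for patients who have chosen reduced contact.

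**If SAE-only collection is intended.** State the exception in 8.7.1. In the SAP, either cut non-serious TEAE tables for all patients at a common point relative to last dose, chosen so that everyone is still under full AE collection, or name the existing Treatment-period tables as the basis for comparing non-serious events between arms. The second choice needs no new output. The cost of either is that late-onset non-serious events drop out of the comparison.
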